6. ANALYSES AND SUMMARIES

6.1. Primary Endpoints

The primary objective of this study is to evaluate the long term safety of tanezumab 10 mg and 5 mg SC administered every 8 weeks (7 administrations). In this section, the safety measures are summarized.

- Adverse events.
- Standard safety assessments (safety laboratory testing [chemistry, and hematology], vital signs).
- Orthostatic (supine/standing) blood pressure assessments.
- Survey of Autonomic Symptoms (SAS) scores.
- Electrocardiogram (ECG, 12-lead) assessments.
- Joint Safety adjudication outcomes.
- Total joint replacements.
- Neurologic examination (Neuropathy Impairment Score [NIS]).
- Outcome of consultation
- Anti-drug antibody assessments (ADA).
- Physical examinations.

Pfizer standard safety data presentations will be made for demography data, discontinuation data, adverse event data, laboratory test data, vital signs data and ECG data.

Adverse events (AEs), concomitant medications, laboratory safety tests, physical and neurological examinations (NIS), vital signs, electrocardiogram (ECG), and the Anti-Drug Antibody (ADA) test will be collected for each subject during the study according to the schedule of assessments.

6.1.1. Safety Measures: Adverse Events

Pfizer standard safety data presentations will be made for adverse event data.

The details of Tier-1, Tier-2 and Tier-3 AEs are described in [Section 3.5.1](#).

Treatment-emergent adverse events within Tier-1 will be summarized. The combined Tier-1 adverse events, but not each adverse event will be summarized using Risk Differences between each tanezumab group and celecoxib, together with 95% CI and p-value, using exact methods. Treatment-emergent adverse events within Tier-2 will be summarized using Risk Differences between each tanezumab group and celecoxib, together with 95% CI, using exact methods. There will be no multiplicity adjustment for these significance tests. These tables will be produced for the comparisons of tanezumab 5mg versus celecoxib and tanezumab 10mg versus celecoxib.

The following footnote will be used in the Tier-1 AE tables: “P-values and confidence interval are not adjusted for multiplicity and should be used for screening purpose only. 95% CIs are provided to help gauge the precision of the estimates for Risk Difference.” Similarly the following footnote will be used in the Tier-2 AE tables: “Confidence intervals are not adjusted for multiplicity and should be used for screening purpose only. 95% Confidence intervals are provided to help gauge the precision of the estimates for Risk Difference.”

It should be recognized that most studies are not designed to reliably demonstrate a causal relationship between the use of a pharmaceutical product and an adverse event or a group of adverse events. Except for select events in unique situations, studies do not employ formal adjudication procedures for the purpose of event classification. As such, safety analysis is generally considered as an exploratory analysis and its purpose is to generate hypotheses for further investigation. The 3-tier approach facilitates this exploratory analysis.

Pfizer standard safety data presentations will be made for demography data, concomitant medications, discontinuation data, adverse event data, laboratory test data, vital sign data and ECG data.

The non-standard safety tables as described in [Section 3.5.1](#) will also be summarized. The details are described below.

Summary of AEs, Incidence of AEs, Incidence of AEs leading to discontinuation and summary of Serious AEs will be shown for the whole study period (including the safety follow-up period) will be created.

The following non-standard safety tables will also be included:

- Incidence and severity of adverse events leading to discontinuation.
- Summary of AEs, Incidence of AEs, Incidence of AEs leading to discontinuation and summary of Serious AEs.
- ‘Incidence and severity’ tables of treatment-emergent adverse events of Abnormal Peripheral Sensation (APS), and Sympathetic Nervous system, as defined above. Other adverse events may be added to these groupings if they are observed in this study or other studies in the tanezumab program.
- Adverse events associated with laboratory abnormalities, vital signs, and ECG measurement may be summarized.

6.1.2. Safety Measures: Standard Safety Assessments (safety laboratory testing [chemistry, and hematology], vital signs)

Pfizer standard safety data presentations will be made for laboratory test data and vital signs data. The following non-standard safety tables will also be included:

- A summary of the maximum increase from baseline in the sitting systolic and diastolic blood pressure. The categories used are: (systolic BP) only decreases or no change, >0 to 10, >10-20, >20-30, >30-40, and >40, and (diastolic BP) only decreases or no change, >0 to 10, >10-20, >20-30, and >30.
- A summary of the maximum decrease from baseline in the sitting systolic and diastolic blood pressure. The categories used are: (systolic BP) <-40, -40 to <-30, -30 to <-20, -20 to <-10, -10 to <0, only increases or no change, and (diastolic BP) <-30, -30 to <-20, -20 to <-10, -10 to <0, only increases or no change.
- A summary of the change from baseline to last observation in the sitting systolic and diastolic blood pressure. The categories used for these summaries are: (systolic BP) \leq -40, >-40 to -30, >-30 to -20, >-20 to -10, >-10 to 0, >0 to <10, 10-<20, 20-<30, 30-<40, \geq 40, and (diastolic BP) \leq -30, >-30 to -20, >-20 to -10, >-10 to 0, >0 to <10, 10-<20, 20-<30, \geq 30.

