7.4.3. Orthostatic Hypotension and Sympathetic Function Adverse Events

Blood pressure changes meeting the pre-specified criteria for orthostatic hypotension and confirmed as described in Section 7.3.5.1 will be designated as confirmed orthostatic hypotension episode and should be reported as an adverse event whether or not the subject had accompanying symptoms.

Confirmed episodes of orthostatic hypotension: If a confirmed episode of orthostatic hypotension occurs (as defined in Section 7.3.5.1) it should be reported as an adverse event and the subject should be further evaluated as described below to determine if a neurology or cardiology consultation should be obtained and/or whether further treatment with investigational product should occur. Figure 6 provides a flow diagram for the processes described below.

1. If no apparent medical cause (eg, dehydration, illness, medications) is identified at the time the orthostatic hypotension criterion is met and the subject is symptomatic, the subject should be further evaluated for the presence of sympathetic autonomic neuropathy by a cardiologist or neurologist as soon as possible. See “Sympathetic function adverse events” below for decisions regarding subject management and continued dosing with investigational product.
2. If an apparent medical cause is identified at the time the orthostatic hypotension criterion is met or if subject is asymptomatic, the subject should have a repeat assessment of orthostatic hypotension performed at least 1 week later but not more than 4 weeks later. During this time the investigator should attempt to address the underlying medical cause of the orthostatic hypotension. If confirmed orthostatic hypotension (as defined in Section 7.3.5.1) is present at the follow-up visit, the subject should be further evaluated for the presence of sympathetic autonomic neuropathy by a cardiologist or neurologist as soon as possible. See “Sympathetic function adverse events” below for decisions regarding subject management and repeat dosing.

[figure not shown]
Sympathetic function adverse events: Subjects reporting adverse events (any seriousness or severity) with preferred terms of bradycardia (see Section 7.3.6 for ECG criteria for

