9.2. Analysis of Safety Endpoints

- Adverse events, concomitant medications, laboratory safety tests, physical and neurological examinations, vital signs, electrocardiogram (ECG), and the anti-drug antibody test will be collected for each subject during the study according to the Schedule of Assessments. Standard safety reporting tables will summarize and list the safety data.
- Adverse events of interest and common adverse events will be summarized using Risk Differences between each tanezumab group and the celecoxib group, together with 95% confidence interval, using exact methods.
- Separate adverse event summaries by treatment group for adverse events of decreased sympathetic function will be conducted. More specifically, adverse events with the following preferred terms will be considered to represent adverse events of decreased sympathetic function: Blood pressure orthostatic decreased, bradycardia, dizziness postural, heart rate decreased, orthostatic hypotension, presyncope, sinus bradycardia, syncope, anhidrosis, hypohidrosis, abdominal discomfort, diarrhea, early satiety, fecal incontinence, nausea, vomiting, ejaculation delay, ejaculation disorder, ejaculation failure, hypertonic bladder, micturition urgency, nocturia, urinary frequency, urinary hesitation, urinary incontinence, respiratory distress and respiratory failure. If

² Details are described in [section 9.2](#).

necessary, this list of preferred terms may be adjusted for updates made to the MedDRA dictionary versions used for reporting.

- In addition to summaries of adverse events considered to represent adverse events of decreased sympathetic function noted above, adverse events of syncope, bradycardia, orthostatic hypotension, anhidrosis, or hypohidrosis are designated as adverse events of interest that will be reviewed by the unblinded E-DMC (See Section 9.6).
- Incidence of orthostatic hypotension using postural changes in blood pressure, in addition to mean changes in postural blood pressure will be summarized.
- The SAS scores will be summarized by treatment group for the total number of symptoms reported and total impact score. The summary will be shown by visit, and for the change from Baseline.

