3.5. Safety Endpoints

3.5.1. Adverse Events

An adverse event is considered treatment emergent relative to a given treatment if:

- The event occurs for the first time during the effective duration of treatment and was not seen prior to the start of treatment, or
- The event was seen prior to the start of treatment but increased in severity during treatment.

A 3-tier approach will be used to summarize AEs. Under this approach, AEs are classified into 1 of 3 tiers. Different analyses will be performed for different tiers (See [Section 6.1.1](#)).

Tier-1 events: These are pre-specified events of clinical importance. Tier-1 events include syncope, bradycardia, orthostatic hypotension, anhidrosis, hypohidrosis.

Tier-2 events: These are events that are not Tier-1 but are “common”. A MedDRA PT is defined as a Tier-2 event with a frequency of $\geq 3\%$ in any treatment group.

Tier-3 events: These are events that are neither Tier-1 nor Tier-2 events, and will be summarized using standard Pfizer data standards tables, where all Adverse Events will be included (ie, Tier-3 AEs will not be shown separately).

The adverse events of Abnormal Peripheral Sensation (APS) are defined in the table below.

| | |
|------------------------------|------------------------------------|
| Allodynia | Neuritis |
| Axonal neuropathy | Neuropathy peripheral |
| Burning sensation | Paraesthesia |
| Carpal Tunnel Syndrome | Paraesthesia oral |
| Decreased Vibratory Sense | Peripheral sensorimotor neuropathy |
| Demyelinating polyneuropathy | Peripheral sensory neuropathy |
| Dysaesthesia | Polyneuropathy |
| Formication | Polyneuropathy chronic |
| Hyperaesthesia | Sensory disturbance |
| Hyperpathia | Sensory loss |
| Hypoaesthesia | Thermohypoaesthesia |
| Hypoaesthesia oral | Sciatica |
| Intercostal neuralgia | Tarsal Tunnel Syndrome |
| Neuralgia | |

Adverse Events of Sympathetic Nervous System are defined in the table below.

| | |
|--------------------------------------|-------------------------|
| Abdominal discomfort | Micturition urgency |
| Anal incontinence | Nausea |
| Anhidrosis | Nocturia |
| Blood pressure orthostatic decreased | Orthostatic hypotension |
| Bradycardia | Pollakiuria |
| Diarrhoea | Presyncope |
| Dizziness postural | Respiratory distress |
| Early satiety | Respiratory failure |
| Ejaculation delayed | Sinus bradycardia |
| Ejaculation disorder | Syncope |
| Ejaculation failure | Urinary hesitation |

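### The five Tier-1 events of interest get a risk difference and interval only as a pool, while any other term at 3% or more gets its own

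*SAP*

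**What the plan says.** SAP 3.5.1 sets the tiers. "Tier-1 events include syncope, bradycardia, orthostatic hypotension, anhidrosis, hypohidrosis". Tier-2 is introduced with the words "These are events that are not Tier-1 but are" common, and the cut-off follows: "A MedDRA PT is defined as a Tier-2 event with a frequency of" at least 3% in any treatment group.

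SAP 6.1.1 sets the analyses. For Tier-1: "Treatment-emergent adverse events within Tier-1 will be summarized", and then "The combined Tier-1 adverse events, but not each adverse event will be summarized using Risk Differences between each tanezumab group and celecoxib", with a 95% interval and a p-value by exact methods. For Tier-2: "Treatment-emergent adverse events within Tier-2 will be summarized using Risk Differences between each tanezumab group and celecoxib, together with 95% CI, using exact methods", with no p-value. Both sets are produced for 5 mg versus celecoxib and for 10 mg versus celecoxib, under a footnote that labels them unadjusted and for screening only.

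Protocol 9.2 covers both classes in one sentence: "Adverse events of interest and common adverse events will be summarized using Risk Differences between each tanezumab group and the celecoxib group", with 95% intervals by exact methods. The same section designates the five terms that the SAP calls Tier-1 as adverse events of interest.

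The SAP version history shows that restricting the interval and p-value to the pool was a deliberate change in version 2 (June 2019). The rationale given there is general to that version; none is specific to this change.

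**The concern.** The five terms were singled out in advance as clinically important, and adverse events are a primary endpoint. Yet the tier rules give a term-level between-group estimate with its precision to ordinary common terms and withhold it from these five. A reader of the final report will have counts by arm for syncope, but no planned risk difference or interval for it.

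A pooled estimate is a poor substitute when its components behave differently. Orthostatic hypotension is sought by scheduled supine and standing readings, and under Protocol 7.4.3 a confirmed episode "should be reported as an adverse event whether or not the subject had accompanying symptoms". Syncope has no such scheduled measurement. If one component is balanced between arms, it adds noise to a difference in another. If two components differ in opposite directions, the pool can show nothing.

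**Working it through.** **1. The plan's own figure, for scale.** Protocol 9.1 assumes a 6% rate of decreased-sympathetic-function events and states that 4 to 10 of about 113 tanezumab subjects would have one with probability of at least 80%. Exact binomial: P(4 ≤ X ≤ 10), n = 113, p = 0.06, is 0.836. For 6 to 14 of 170 it is 0.858. Both agree with the Protocol. In one arm of 66, 0.06 × 66 = 3.96, so about 4 subjects are expected over the whole sympathetic list in Protocol 9.2. The five Tier-1 terms are only part of that list, so counts per term should be small.

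**2. When a Tier-2 term gets its own interval.** The threshold is 3% in any arm; planned arm size is about 66 (56 to 73).
- 0.03 × 56 = 1.68, so 2 subjects
- 0.03 × 66 = 1.98, so 2 subjects
- 0.03 × 73 = 2.19, so 3 subjects

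For a Tier-1 term no count is enough, because Tier-2 excludes it by definition.

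**3. What pooling can do.** The documents give no counts by term, so these are assumed: 66 per arm, no subject with two of the events. The interval is exact unconditional, based on the score statistic, with two one-sided 2.5% limits.

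*Dilution (orthostatic hypotension balanced at 4 v 4):*
- Syncope 5 v 0: 5/66 - 0/66 = +7.6 points (1.4 to 16.8). Pooled 9 v 4: 13.6 - 6.1 = +7.6 (-3.0 to 19.1).
- Syncope 3 v 0: 3/66 - 0/66 = +4.5 points (-1.1 to 12.9). Pooled 7 v 4: 10.6 - 6.1 = +4.5 (-5.7 to 15.4).

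*Cancellation:*
- Orthostatic hypotension 5 v 0: +7.6 (1.4 to 16.8).
- Bradycardia 0 v 5: -7.6 (-16.8 to -1.4).
- Pooled 5 v 5: 0.0 (-10.2 to 10.2).

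**4. How far this depends on the interval method.** The SAP says exact methods without naming one. Fisher's two-sided p for 5 v 0 is 0.058, so whether zero is excluded at that count depends on the method. An exact interval that orders tables by the raw difference depends only on that difference, so 5 v 0 and 9 v 4 would get the same interval and the dilution contrast would vanish. The cancellation example does not depend on the method, because the point estimates themselves (+7.6, -7.6 and 0.0) differ.

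**The case against.** The strongest reply is that Protocol 9.2 does not promise a risk difference for each event. The word 'each' there attaches to the tanezumab group, so a pooled estimate for the events of interest arguably satisfies it. Protocol 9 and SAP 2 also let the SAP modify the plan, with an amendment needed only for a major change to a primary endpoint or its analysis; whether this is one is a matter of judgement. This stands. A reader might infer that the SAP breaches the Protocol, but the text does not support that.

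A reader might also infer that these events get less analysis than common ones, or no planned estimate of any kind. The documents do not support this either. Tier-1 has a pooled estimate for each dose, and a p-value that Tier-2 lacks. The five terms appear in the Tier-1 summary and in the incidence-and-severity tables for the sympathetic list (SAP 6.1.1). Orthostatic hypotension is tabulated by visit and for any post-baseline occurrence (SAP 6.1.3), and sympathetic neuropathy assessments are summarised (SAP 6.1.8). The external data monitoring committee reviews these five terms unblinded (Protocol 9.6). What is missing is specifically the event-level risk difference and its interval.

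The pool is also not arbitrary: Protocol 7.4.3 sends all five events to the same evaluation. Nor can it be assumed that orthostatic hypotension will dominate. It must be confirmed on repeat sequences (Protocol 7.3.5.1), subjects who have it at screening are excluded, and bradycardia is likewise reported when ECG criteria are met (Protocol 7.3.6).

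Finally, it is tempting to say that sinus bradycardia, heart rate decreased and blood pressure orthostatic decreased leak out of the pool and belong in Tier-1. Protocol 7.3.5.1 and 7.3.6 direct qualifying cases to orthostatic hypotension and bradycardia, which are Tier-1 terms. Protocol 9.2 does not list the synonyms as events of interest, and they stay in the sympathetic tables. No change to Tier-1 membership is warranted.

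**Conclusion.** The point holds in a limited form. The tier rules leave the five designated events of interest without an event-level risk difference or interval, while any other term at 3% or more (2 of 66 subjects) has both. This is narrower than the natural reading of a Protocol sentence that treats events of interest and common events alike, and no specific reason is given.

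The size of the effect cannot be fixed from the documents. The illustrations rest on assumed counts, 66 per arm and no overlap; the dilution example also rests on a score-based exact interval. The 9 v 4 pool is well above the roughly 4 per arm that the planning rate implies for the whole sympathetic list, so it shows what pooling can do and is not a forecast. At 3 v 0 even the single-term interval includes zero. No formal hypothesis is tested (SAP 5.1), so no trial conclusion turns on this. It is a cheap improvement to the reporting of a primary safety endpoint.

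**What to change.** In SAP 6.1.1, keep the pooled Tier-1 analysis as written. Add, for each of the five Tier-1 preferred terms, the risk difference and exact 95% interval for 5 mg versus celecoxib and for 10 mg versus celecoxib. Mark these rows descriptive, give no p-values, and use the same exact method as for Tier-2. The existing screening-only footnote already covers them. Leave Tier-1 membership unchanged.

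The cost is a change of wording and five rows in an existing table for each dose comparison: 5 terms × 2 comparisons = 10 more unadjusted intervals. Most will be wide, and terms with few or no events will be uninformative. No new data are needed.

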6.1.3. Safety Measures: Orthostatic (supine/standing) Blood Pressure Assessments

The following non-standard safety tables will be included

- Incidence of subjects with orthostatic hypotension (defined in [Section 3.5.3](#) above), for each visit and any post-baseline of orthostatic hypotension. An additional summary will be provided of outcomes of assessments resulting from an incident of orthostatic hypotension or other events of interest, using data from both the CRF database and the consultation database, as appropriate.

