2.2. Endpoints

2.2.1. Primary Endpoints

Safety Measures

- Adverse events.
- Standard safety assessments (safety laboratory testing [chemistry, and hematology], vital signs).
- Orthostatic (supine/standing) blood pressure assessments.
- Survey of Autonomic Symptoms (SAS) scores.
- Electrocardiogram (ECG, 12-lead) assessments.
- Joint Safety adjudication outcomes.
- Total joint replacements.
- Neurologic examination (Neuropathy Impairment Score [NIS]).
- Anti-drug antibody assessments (ADA).
- Physical examinations.

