7.3.5.1. Orthostatic Blood Pressure Measurements

In addition to sitting vital sign measurements, orthostatic blood pressure measurements will be obtained using a standard manual sphygmomanometer at Screening, Baseline and at Weeks 2, 4, 8, 16, 24, 32, 40, 48, 56, 64 and 80 (or Early Termination). At each of these clinic visits, blood pressure will be assessed in supine and standing positions. Orthostatic blood pressure measurements will be obtained after collection of the sitting vital signs and before any required phlebotomy (and prior to dosing at dosing visits). To minimize chances of orthostatic hypotension related to volume depletion, subjects should be reminded to report for clinic visits well hydrated. In this regard, investigators could consider recommending to subjects that they consume 8-16 ounces (240-480 mL) of water prior to reporting to the clinic for study visits. All orthostatic blood pressure measurements will be recorded in the IRT system.

Supine blood pressure measurement will be obtained after subjects have been in the supine position for a minimum of 10 minutes. To ensure that a stable supine blood pressure measurement is obtained, at least two systolic and diastolic measurements will be performed. If the replicate systolic and diastolic measurements differ by no more than 10 mmHg and 5 mmHg, respectively, the supine blood pressure will be considered to be stable. The mean of the two stable replicate measures will be considered to represent the baseline supine blood pressure (mean systolic and mean diastolic blood pressure) for that visit. Once the supine blood pressure is considered to be stable, subjects will be asked to assume the standing position. After subjects have been in the standing position for 1 minute and 3 minutes, systolic and diastolic blood pressure will be measured and recorded for both timepoints. If the measurements do not meet the criteria for orthostatic (postural) hypotension, no further measurements are needed. If either the 1 minute or 3 minute standing blood pressure measurements show decreases meeting the criteria shown in [Table 5](#), the sequence of supine and standing measurements should be repeated up to 2 more times. Refer to [Table 5](#) for the criteria defining orthostatic hypotension and actions that should be taken when orthostatic hypotension criteria are met.

Table 5. Orthostatic Blood Pressure Changes and Subject Management

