| | | | 
 • Section 5.3: Added the analysis with multiple imputation, BOCF and LOCF for the summary for LBPI, RMDQ, PGA and BPI-sf. • Section 6.1.1: P-value and 95% CI for risk difference will be shown for pooled Tier 1 adverse events and will not be shown for each adverse event within Tier 1 event. Updated the description of footnote for 3-tier AE tables. Removed the following analyses: Tier 1 and Tier 2 AE graphs, the comparison between the number of subjects with AEs of APS against the number of subjects with the AE of Oedema peripheral, the plots of the start and stop study day of specified individual AES of APS, the summary of start day and AE duration for five AEs of APS (Paraesthesia, Hyperaesthesia, Hypoaesthesia, Allodynia and Dysaesthesia), AEs of DSF and Oedema peripheral, summary of AEs and serious AEs by 1000 patient years of exposure, ‘incidence and severity’ table for decreased sympathetic function (DSF), and listing of AEs for subjects who are not randomized and those randomized and not treated. Added the summary for adverse events associated with laboratory abnormalities, vital signs, and ECG measurement. • Section 6.1.2: Changed the category of blood pressure. • Section 6.1.3: Removed the summary of mean change in postural blood pressure. Clarified the detail of analysis. • Section 6.1.6: Updated the analysis plan for joint safety adjudication outcomes and total joint replacement. • Section 6.1.7: Separate section (6.1.8) was made for outcome of consultation and moved the description on outcome of consultation to Section 6.1.8. • Section 6.1.9: Specified that ADA assessments will be made using all available data. • Section 6.1.10: Updated the analysis plan for physical examination. • Section 6.2: Clarified the definition of ‘on-treatment’ and ‘off-treatment’. |
|--|--|--|---|

| | | | |
|--|--|--|---|

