2. INTRODUCTION

This SAP provides the detailed methodology for summary and statistical analyses of the data collected in study A4091063. This document may modify the plans outlined in the protocol; however, any major modifications of the primary endpoint definition or its analysis will also be reflected in a protocol amendment.

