3.5.3. Orthostatic (supine/standing) Blood Pressure Assessments

The incidence of orthostatic hypotension at each visit, at the last visit and for any post-baseline incidence will be summarized. The definition of orthostatic hypotension to be summarized is:

- For patients with Baseline supine systolic Blood Pressure ≤ 150 mmHg:
 - Reduction in sBP (standing minus supine) ≥ 20 , OR
 - Reduction in dBP (standing minus supine) ≥ 10 .
- For patients with Baseline supine systolic Blood Pressure > 150 mmHg:
 - Reduction in sBP (standing minus supine) ≥ 30 , OR
 - Reduction in dBP (standing minus supine) ≥ 15 .

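### The SAP omits the mean postural blood pressure changes that protocol 9.2 commits to, so an average drop below the threshold would appear in no specified table of measured postural pressure

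*SAP*

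**What the plan says.** Protocol 2.2.1 lists "Orthostatic (supine/standing) blood pressure assessments" among the primary endpoints. Protocol 9.2 then sets out the analysis: "Incidence of orthostatic hypotension using postural changes in blood pressure, in addition to mean changes in postural blood pressure will be summarized".

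SAP 3.5.3 says: "The incidence of orthostatic hypotension at each visit, at the last visit and for any post-baseline incidence will be summarized". It defines the outcome as a systolic or a diastolic fall beyond a cut-point that depends on supine systolic pressure. SAP 6.1.3 gives incidence "for each visit and any post-baseline of orthostatic hypotension" and one further output: "An additional summary will be provided of outcomes of assessments resulting from an incident of orthostatic hypotension or other events of interest". Neither section mentions a mean.

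The SAP version history, under version 2, records "Removed the summary of mean change in postural blood pressure". I use that entry only as evidence that the omission was deliberate; the point rests on the current text of the two documents. The entry gives no reason of its own. The general rationale for version 2 cites the protocol amendment, blinded data review and alignment across the programme.

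Protocol 7.3.5.1 schedules the readings at Screening, "Baseline and at Weeks 2, 4, 8, 16, 24, 32, 40, 48, 56, 64 and 80". Each visit has at least two supine readings, then standing readings at 1 and 3 minutes, all recorded electronically.

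**The concern.** The protocol promises a continuous summary of a primary safety assessment and the SAP does not provide it. What remains is a threshold count. If tanezumab lowered standing pressure by a few mmHg on average without pushing many subjects past the cut-point, the count would respond weakly and no listed table of measured postural pressure would display the shift. Protocol 9.1 names decreased sympathetic function as one of two neurological safety questions that this trial should be able to evaluate, so the measurement is not peripheral.

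**Working it through.** **Step 1: does another specified table supply the mean?**

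- SAP 6.1.2 tabulates changes in *sitting* systolic and diastolic pressure, in categories. Sitting pressure is not postural change.
- The second output of SAP 6.1.3 covers outcomes of assessments after an incident.
- Orthostatic hypotension also enters the combined Tier-1 adverse events (SAP 3.5.1 and 6.1.1), again as yes/no.
- The sponsor's standard vital-sign tables are not itemised. They cannot be assumed to hold a summary that the version history says was removed.

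So no specified table fills the gap. By contrast, autonomic symptom scores (SAP 6.1.4) and the neuropathy score (SAP 6.1.7) are both summarised as continuous changes.

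**Step 2: what might the mean add?**

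The plan states no figure for postural pressure that could be reproduced. The calculation below is an illustration on assumptions.

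From the documents: about 66 subjects per arm (protocol 9.1), 11 post-baseline visits (protocol 7.3.5.1), and a positive result for a systolic fall of at least 20 or a diastolic fall of at least 10 mmHg (SAP 3.5.3, supine systolic up to 150).

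Assumed: normal standing-minus-supine changes; systolic mean -3 mmHg with SD 8, 10 or 12; diastolic mean 0 with SD 5, 6 or 7; extra falls of 3 mmHg systolic and 1.5 mmHg diastolic in one arm; systolic-diastolic correlation 0.5; correlation between visits (ρ) 0.3 or 0.5; correlation between the 1- and 3-minute readings 0.8; either standing reading counts; no confirmation repeat; all visits attended.

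*Mean, one visit:* z = 3 / (SD × √(2/66)), with √(2/66) = 0.1741.
- SD 8: 3/1.393 = 2.15
- SD 10: 3/1.741 = 1.72
- SD 12: 3/2.089 = 1.44

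*Mean averaged over k visits:* divide by √[(1 + (k-1)ρ)/k].
- Most favourable: SD 8, k = 11, ρ = 0.3. The factor is √(4.0/11) = 0.603, so z = 2.15/0.603 = 3.57.
- Least favourable: SD 12, k = 5, ρ = 0.5. The factor is √(3/5) = 0.775, so z = 1.436/0.775 = 1.85.

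*Incidence:* p0 (no shift) and p1 (shift) are simulated, then z = (p1 - p0)/√{[p0(1-p0) + p1(1-p1)]/66}. Without the shift, single-visit incidence is about 6%, 12% and 19% for the three SD pairs. For any post-baseline occurrence over k visits:

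| SD sys/dia | ρ | k | p0 / p1 | z, incidence | z, averaged mean | squared ratio |
|---|---|---|---|---|---|---|
| 8/5 | 0.3 | 5 | 21.7% / 37.2% | 1.97 | 3.25 | 2.7 |
| 8/5 | 0.3 | 11 | 35.7% / 55.9% | 2.38 | 3.57 | 2.3 |
| 8/5 | 0.5 | 11 | 28.4% / 45.1% | 2.01 | 2.92 | 2.1 |
| 10/6 | 0.3 | 11 | 58.2% / 73.8% | 1.91 | 2.86 | 2.2 |
| 10/6 | 0.5 | 5 | 33.9% / 47.6% | 1.62 | 2.22 | 1.9 |
| 12/7 | 0.3 | 11 | 73.0% / 83.6% | 1.49 | 2.38 | 2.6 |
| 12/7 | 0.5 | 5 | 46.8% / 58.7% | 1.38 | 1.85 | 1.8 |

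The averaged mean is the more precise in every row. The single-visit mean (1.44 to 2.15) is about level with any-visit incidence (1.4 to 2.4).

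**Step 3: precision of a restored contrast.** The 95% half-width for a between-arm difference in means at one visit is 1.96 × SD × 0.1741, or 2.7, 3.4 and 4.1 mmHg for SD 8, 10 and 12.

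**The case against.** *The SAP may modify the protocol.* It may. Only a major change must go further: "any major modifications of the primary endpoint definition or its analysis will also be reflected in a protocol amendment". A reader might infer that dropping this summary breaches that rule. The documents do not settle it: the endpoint and its incidence analysis stay, no hypothesis is tested (SAP 5.1), and the removal is disclosed. Whether one descriptive summary is major is a judgement. The mismatch between the two texts stands either way.

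*Incidence will be rare, so the mean carries 3 to 7 times the information.* A reader might infer this from the exclusion of orthostatic hypotension at entry and a simple calculation. Testing one systolic reading against -20 mmHg at one visit gives incidence of 1.7% v 4.0%, 4.5% v 8.1% and 7.8% v 12.2% for SD 8, 10 and 12. The z-values are 0.81, 0.86 and 0.83, and the squared ratios against the mean are 7.1, 4.0 and 3.0. But the planned outcome also counts diastolic falls and any post-baseline visit, and there are two standing readings at each visit. Modelled that way it is not rare and the advantage shrinks. The confirmation rule in protocol Table 5 would lower incidence again, but SAP 3.5.3 does not state that rule. The multiple is therefore not established.

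*The trial loses its most sensitive autonomic measure.* Nothing in the documents ranks these measures. The SAP keeps continuous autonomic symptom scores, the Tier-1 and sympathetic adverse events, ECG heart rate and consultation outcomes.

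*Sixty-six per arm will not last.* This stands. Expected completion of 34% to 54% leaves about 22 to 36 per arm, where the single-visit z is only about 0.8 to 1.6, in subjects selected for Week 16 response. Late-visit means will be imprecise and need careful reading.

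*Adjusted contrasts exceed the commitment.* This also stands. Protocol 9.2 promises a summary. Two pressures × two standing times × 11 visits × two contrasts would be 88 intervals.

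**Conclusion.** The point holds as a protocol-SAP inconsistency with a cheap remedy. The SAP does not deliver a committed summary of a primary safety assessment, and no other specified table shows an average postural shift below the threshold. That conclusion needs no assumption.

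The gain in precision does rest on assumptions. Under those listed, the visit-averaged mean carries roughly 1.8 to 2.7 times the information of any-visit incidence. It rests on normality, the assumed SDs and correlations, full attendance and no confirmation repeat. The z-values illustrate precision only, since the study is descriptive. The documents do not support calling the outcome rare, fixing the gain at 3 to 7 times, or treating a protocol amendment as clearly required.

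**What to change.** Restore to SAP 6.1.3, and mirror in 3.5.3, a descriptive table by arm and visit of standing-minus-supine systolic and diastolic pressure at 1 and 3 minutes, with n, mean, SD, 95% CI and change from Baseline.

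Use the first measurement sequence at each visit. Protocol 7.3.5.1 repeats the sequence only when the first meets the criteria, so pooling sequences would make the number of readings depend on the result.

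An unadjusted difference in mean change for each tanezumab arm versus celecoxib, with 95% CI, is an optional extension beyond what the protocol promises.

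The cost is one or two extra tables from data already collected. No visit, procedure or clinical rule changes.
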